### **I.3 Multivariate analysis**

To study the effect of the two methods on the different outcome measures, additional multivariate analysis will be applied, as described below.

Logistic regression will be applied to assess differences of accuracy between the two methods, adjusted for; age, indication, number of needle passes, vial number, and the presence of an on-site pathologist.

Ordinal logistic regression will be applied to assess differences of quality and presence of tissue cores between the two methods, adjusted for; age, indication, number of needle passes, vial number and the presence of an on-site pathologist.

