## SUMMARY

**Rationale:** During Endoscopic Ultrasound (EUS), tissue samples can be obtained with different techniques. Fine needle aspiration (FNA) provides a cytological specimen. With fine needle biopsy (FNB), a histological specimen is obtained, which generally results in a better diagnostic performance. However, FNB needles are stiffer and more difficult to handle, and can therefore result in less tissue acquisition.

**Objectives:** To compare the performance and diagnostic accuracy of two EUS-guided tissue acquisition devices; a 25G Echotip Ultra Fine Needle Aspiration (FNA) device and a new, more flexible 20G Echotip ProCore Fine Needle Biopsy (FNB) device.

**Study design:** International randomized multicenter trial.

**Study population:** Patients  $\geq 18$  years old, referred for EUS-guided tissue sampling of a: (I) pancreatic mass lesion, (II) lymph node, or (III) other submucosal or undefined mass (non-pancreatic),  $\geq 1$  cm in size.

**Intervention:** EUS-guided tissue acquisition by means of either the 25G Echotip Ultra FNA device, or the 20G Echotip ProCore FNB device.

**Main study parameters/endpoints:** The main endpoint is the diagnostic performance, measured against the *gold standard* diagnosis (based on the surgical resection specimen or in non-operated patients, the outcome of the diagnostic work-up (i.e. tissue sampling and imaging studies), confirmed by a compatible clinical disease course). Secondary endpoints include I. technical success, II, specimen specifics, such as; quality, presence of tissue cores, and pathological classification (cytology, cell-block, or histology), III. procedural aspects, such as; safety, the yield of a single needle pass, and the value of on-site pathological evaluation, and IV. inter-observer variation.

**Nature and extent of the burden and risks associated with participation, benefit and group relatedness:** There are no additional risks involved. Patients are referred for EUS-guided tissue acquisition, as part of the standard diagnostic work-up. Previous reports showed EUS-guided FNA and FNB sampling to be equally safe.

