### **I.2 Univariate analysis**

#### **I.2.1 Primary endpoint**

Overall diagnostic accuracy will be compared between the two groups, using the Pearson's chi-squared test. Additionally, the p-value, adjusted by strata, will be calculated.

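### Both regressions in SAP I.3 adjust the needle comparison for number of passes, which is observed only after needle assignment, so their odds ratios may not be total needle effects

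*SAP*

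**What the plan says.** SAP I.3 gives the purpose of the models: "To study the effect of the two methods on the different outcome measures, additional multivariate analysis will be applied, as described below". The accuracy model is a logistic regression "adjusted for; age, indication, number of needle passes, vial number, and the presence of an on-site pathologist". The second model has the same covariates: "Ordinal logistic regression will be applied to assess differences of quality and presence of tissue cores between the two methods, adjusted for; age, indication", followed by passes, vial number and on-site pathologist.

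The primary analysis in SAP I.2.1 does not use these covariates: "Overall diagnostic accuracy will be compared between the two groups, using the Pearson's chi-squared test". It is supplemented by an adjustment for strata only: "Additionally, the p-value, adjusted by strata, will be calculated".

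Two statements in the Protocol Summary bear on whether passes could differ by arm. The rationale says of FNB needles in general that "FNB needles are stiffer and more difficult to handle, and can therefore result in less tissue acquisition", although the trial's own FNB device is described as more flexible. The secondary endpoints include "the yield of a single needle pass, and the value of on-site pathological evaluation".

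The supplied text does not fix the number of passes, give a rule for stopping, define vial number, or say that I.3 is meant to compare the needles at equal numbers of passes.

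**The concern.** The needle is randomised, and the number of passes is a consequence of the procedure done with it. Conditioning on a variable that treatment may affect does two things. It removes any part of the needle effect that acts through passes. It can also create an association between needle and lesion difficulty: if hard lesions need more passes and one needle needs fewer passes overall, patients with the same pass count in the two arms are not equally difficult. Age and a broad indication category cannot be assumed to correct this.

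The I.3 odds ratios would be read as needle effects on accuracy, quality and tissue cores. They could show a difference where none exists, or hide, shrink or enlarge a real one. The plan gives no rule for reading a disagreement with the main tests.

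The same question arises for vial number if it is a count of vials. If it indexes samples within a patient, the term may be legitimate, but the data then have several rows per patient and a plain logistic model ignores the clustering.

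**Working it through.** The plan gives no sample size, accuracy rates or pass counts, so there is no figure to reproduce. Every input below is assumed. The purpose is to show when the two odds ratios (ORs) part, and by how much.

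**Exact enumeration (no sampling error).** Passes = 1 + Binomial(3, π). Logit(accuracy) = 1.0 + b·FNB + c·(passes − 2) − d·U, where U is an unmeasured marker of a difficult lesion, present in half the patients.

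*Effect through passes.* Take b = 0.5, c = 0.5, d = 0, with π = 0.6 for FNA and 0.3 for FNB, so mean passes are 1 + 3(0.6) = 2.8 and 1 + 3(0.3) = 1.9.
- FNA accuracy: 0.064(0.6225) + 0.288(0.7311) + 0.432(0.8176) + 0.216(0.8808) = 0.794.
- FNB accuracy: 0.343(0.7311) + 0.441(0.8176) + 0.189(0.8808) + 0.027(0.9241) = 0.803.
- Total OR = (0.803/0.197)/(0.794/0.206) = 1.06. Passes-adjusted OR = exp(0.5) = 1.65.
- With the two π values exchanged, so that FNB uses more passes, the total OR is 2.51 and the adjusted OR is again 1.65.

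*Association through difficulty.* Take b = 0, c = 0, d = 2, with π = 0.45 (easy) and 0.85 (difficult) for FNA, 0.25 and 0.65 for FNB. Accuracy is 0.500 in both arms, so the total OR is 1.00. Among patients with exactly two passes:
- Difficult share, FNA: 3(0.85)(0.15²) / [3(0.85)(0.15²) + 3(0.45)(0.55²)] = 0.0574/0.4658 = 12%.
- Difficult share, FNB: 3(0.65)(0.35²) / [3(0.65)(0.35²) + 3(0.25)(0.75²)] = 0.2389/0.6608 = 36%.

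At equal passes the FNB group is harder, and the fitted passes-adjusted OR is 0.68. When FNB uses more passes by the same margin it is 1.46.

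*Passes equal by arm.* Total and adjusted ORs are 1.63 and 1.65, or 1.58 and 1.58 when difficulty also raises passes. The first small gap is non-collapsibility of the OR, not bias.

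**Simulation.** 2,000 trials per scenario, 300 per arm. Difficulty has variance 1, with 30% explained by a three-level indication. Passes are geometric, capped at 6, with logit(stop) = −0.3 + a·FNB − 1.0·difficulty. Logit(accuracy) = 1.5 + b·FNB − 1.0·difficulty, with b = 0 or 0.6. Both models contain age and indication; arrows show the change when passes are added.

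| Mean passes, FNB vs FNA | OR, no true effect | Null trials significant | OR, true benefit | Power |
|---|---|---|---|---|
| 2.5 vs 2.5 | – | 4.8% → 5.0% | 1.74 → 1.76 | – |
| 2.05 vs 2.5 | 1.00 → 0.90 | 5.9% → 8.6% | 1.72 → 1.56 | 68% → 51% |
| 1.7 vs 2.5 | 1.01 → 0.82 | 5.2% → 15.6% | 1.74 → 1.44 | 72% → 35% |
| 3.3 vs 2.5 | 1.00 → 1.20 | 5.2% → 14.9% | 1.73 → 2.10 | 70% → 89% |

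With the difficulty terms set to zero and 0.5·(passes − 2) added to logit(accuracy), the OR moves from 0.75 to 1.00 (FNB fewer passes), 1.44 to 1.00 (FNB more passes), and 1.38 to 1.85 (FNB fewer passes plus a direct benefit).

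Repeat runs gave ORs within 0.02 of these and null significance rates within about 2 percentage points. At 200 per arm the ORs are within 0.03, and the null rate with passes in the model is about 11% in the two stronger scenarios.

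**Sensitivity to the difficulty assumption.** With both difficulty coefficients cut from 1.0 to 0.5, the null adjusted ORs are about 0.93 (FNB fewer passes), 0.96 (milder) and 1.07 (FNB more passes), with 5.5% to 6.3% significant. At 0.25 they are 0.98 to 1.02, with 5.3% to 5.8% significant.

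**The case against.** The strongest reply has four parts.

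- **The trigger is not documented.** Nothing supplied says the needle changes the number of passes, and the rationale's remark about stiffness concerns FNB needles in general, whereas the trial device is presented as more flexible. A fixed number of passes in text not supplied would largely remove the problem. This stands, and the conclusion is conditional for that reason. But nothing in hand fixes the number, and treating single-pass yield as an endpoint makes an arm difference plausible.
- **The size depends on the inputs.** The 15% false-positive rates need lesion difficulty to act strongly on both passes and accuracy, and they mostly disappear at half that strength. This also stands. The distortion through passes themselves does not depend on that coefficient.
- **The models are supplementary.** The tests in I.2.1 and I.2.2 are untouched, the covariates are openly listed, and SAP I.6 promises an official analysis plan before database closure. This limits the seriousness, but it does not reconcile the stated aim with the covariate list.
- **Comparing needles at equal passes is a legitimate question.** Agreed. It should be kept under its own label.

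Vial number may be defined in text not supplied, so on that point only a definition is requested.

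**Conclusion.** The concern holds and should be fixed. The I.3 models are described as estimating the needle effect but condition on something observed after needle assignment, with no equal-passes target stated.

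If the needle alters passes, the adjusted OR departs from the total effect in a direction the documents do not settle. Under the assumed inputs the simulated null OR ranged from 0.82 to 1.20 when difficulty acts strongly, and stayed close to 1.00 when it acts weakly. Effects through passes could be removed altogether (0.75 or 1.44 to 1.00). If passes do not differ by arm, there is no material distortion.

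Confidence is high on the principle. The size in this trial is unknown. The calculations cover binary accuracy only; the ordinal models were not simulated, though the same reasoning applies. The primary comparison is not affected.

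**What to change.** In the official analysis plan promised in SAP I.6:

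- Remove number of needle passes from both I.3 models, and adjust for age, indication and the randomisation strata.
- Keep on-site pathologist only if its presence was settled before allocation.
- Define vial number. Drop it if it is a count; if it indexes several samples per patient, account for clustering with GEE or a random patient intercept.
- Report number of passes by arm as an outcome.
- If a passes-adjusted model is retained, label it exploratory and state that it compares the needles at equal passes, not the total effect of assignment.

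The cost is one revised covariate list in each of two models and one definition, with no change to design or data collection. The trade-off is that the equal-passes comparison, which relates to the interest in single-pass yield, becomes exploratory.

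### The supportive adjusted models omit lesion size, a pre-sampling characteristic that must be assessed to apply the 1 cm entry limit; prespecifying it costs little and may help modestly

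*SAP*

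**What the plan says.** The primary comparison in SAP I.2.1 is unadjusted: "Overall diagnostic accuracy will be compared between the two groups, using the Pearson's chi-squared test". A stratified version supplements it: "Additionally, the p-value, adjusted by strata, will be calculated". The available text does not name the strata.

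SAP I.3 then adds regression models, introduced as supportive: "additional multivariate analysis will be applied". The accuracy model is a logistic regression "adjusted for; age, indication, number of needle passes, vial number, and the presence of an on-site pathologist". For the specimen outcomes, "Ordinal logistic regression will be applied to assess differences of quality and presence of tissue cores between the two methods", with the same five covariates.

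The Protocol Summary lists three kinds of target: pancreatic mass lesions, lymph nodes, and a third group that begins "other submucosal or undefined mass (non-pancreatic". A minimum size of 1 cm follows. The natural reading is that the limit applies to all three. Nothing in the available text says whether size is recorded as a number, when, or by which modality.

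SAP I.4 repeats every analysis in three sets: all randomised patients, patients whose puncture gave a diagnostic sample (modified ITT), and patients whose puncture gave any tissue (per protocol).

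**The concern.** A covariate earns its place in an adjusted treatment comparison if it is fixed before the intervention can affect it and may predict the outcome. Lesion size meets the first condition and is a plausible candidate for the second. Apart from lesion type, it is the only lesion characteristic that the Summary uses to define who may enter. Of the five terms listed, only age and indication are clearly patient-level baseline factors. Number of needle passes arises during sampling and cannot serve as baseline adjustment. Presence of an on-site pathologist describes the procedure or the site, and vial number, on its natural reading, also belongs to the procedure.

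Two things are at stake, both modest. One is some power for the needle effect in the adjusted models. The other is correction for a difference in size between arms. That matters most in the modified ITT and per-protocol sets: membership depends on whether sampling succeeded, so randomisation no longer guarantees that the needles were used on lesions of similar size.

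**Working it through.** **Inputs.** The documents give no sample size, accuracy rates, allocation ratio, alpha or power, so there is no planned figure to reproduce. Everything below is assumed: 1:1 allocation, two-sided 0.05, 200, 400 or 600 patients in total, accuracy of 80% vs 90% or 75% vs 85%, and a log odds ratio per SD of size of 0, 0.25, 0.5 or 1.0.

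**Step 1: unadjusted power by formula.** For 200 per arm, 80% vs 90%:

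- SE under the null: √(2 × 0.85 × 0.15 / 200) = 0.0357
- SE under the alternative: √((0.80 × 0.20 + 0.90 × 0.10) / 200) = 0.0354
- z = (0.10 − 1.96 × 0.0357) / 0.0354 ≈ 0.85, so power is 80.2%

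**Step 2: power without and with size.** Simulated logistic Wald tests, 1,500 runs per cell, with the marginal accuracy rates held fixed. Entries are % power, unadjusted → adjusted.

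| N | Accuracy | 0 | 0.25 | 0.5 | 1.0 |
|---|---|---|---|---|---|
| 200 | 80 vs 90 | 48.3 → 49.1 | 49.6 → 50.2 | 50.8 → 52.5 | 50.8 → 57.1 |
| 200 | 75 vs 85 | 40.7 → 40.6 | 41.6 → 41.9 | 39.6 → 41.4 | 42.7 → 47.5 |
| 400 | 80 vs 90 | 80.7 → 80.3 | 80.6 → 80.8 | 82.3 → 83.4 | 80.4 → 85.2 |
| 400 | 75 vs 85 | 70.7 → 70.5 | 70.7 → 71.5 | 70.2 → 71.7 | 72.1 → 78.0 |
| 600 | 80 vs 90 | 93.3 → 93.1 | 93.3 → 93.2 | 93.2 → 93.9 | 94.0 → 95.6 |
| 600 | 75 vs 85 | 86.9 → 86.9 | 88.5 → 88.7 | 86.6 → 87.8 | 85.5 → 91.1 |

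The change runs from −0.4 to +0.8 points at 0 and 0.25, from +0.7 to +1.8 at 0.5, and from +1.6 to +6.3 at 1.0. A single cell has a Monte Carlo SE of at most √(0.5 × 0.5 / 1500) = 1.3 points. Both figures in a cell come from the same simulated data, so their difference is steadier than that.

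**Step 3: where the gain comes from.** For N = 400, 80% vs 90%, mean estimate divided by mean SE:

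- At 0.5: unadjusted 0.835 / 0.299 = 2.79; adjusted 0.866 / 0.305 = 2.84
- At 1.0: unadjusted 0.822 / 0.298 = 2.76; adjusted 0.930 / 0.319 = 2.92

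The SE rises. Power improves because the conditional log odds ratio moves further from zero than its SE grows. A gain in precision appears only on the risk-difference scale: the variance of the standardised risk difference falls by about 2–5% at 0.5 and 10–13% at 1.0.

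**Step 4: chance imbalance among all randomised patients.** The SD of the difference in mean size between arms, in SD units of size, is √(4/N): 0.14, 0.10 and 0.08 for N = 200, 400 and 600. At N = 400, an imbalance of 1.96 × 0.10 ≈ 0.20 SD would shift the log odds ratio by about 0.20 × 0.5 = 0.10, or 0.20 × 1.0 = 0.20. The assumed effect is ln(9) − ln(4) = 0.81. Such an imbalance is uncommon and its effect limited.

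**Step 5: what this does not cover.** The √(4/N) result applies only to the full randomised set. In the modified ITT and per-protocol sets a systematic difference in size is possible, and the documents give nothing from which to size it. The ordinal model was not simulated. The other listed covariates were also left out, so the gain would be smaller where size overlaps with indication.

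**The case against.** The best case against is that this is one reviewer's choice of covariate for a supportive model, with a hypothetical and small benefit. Four stronger statements that a reader might infer are not supported.

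- **That size is measured as a value in everyone.** The Summary shows a threshold, which could be applied as a yes/no check. This stands, and the recommendation is conditional on it.
- **That the limit shows size to be prognostic.** An entry limit may reflect feasibility or the definition of the population, and it says nothing about prognosis above 1 cm. This also stands. Prespecification does not need proof, because the loss if size proves weak is negligible.
- **That omission sacrifices precision in the quoted models.** It does not: adding a prognostic covariate raises the SE of the log odds ratio and makes the estimate a conditional odds ratio.
- **That the primary result is biased.** This is an "International randomized multicenter trial", and its unadjusted chi-squared test is valid without size. Chance imbalance is already reflected in that test's error rate.

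It is also fair to say that the unnamed strata prevent a full account of what is already handled, and that SAP I.6 foresees an official analysis plan before the database closes, so the list is not final. The second point makes the change easy; it does not make it unnecessary.

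**Conclusion.** The point holds as a low-cost improvement to the supportive analyses, not as an error that threatens the trial. Both models in I.3 omit a natural pre-sampling covariate while including at least one term that arises during sampling. On the assumed inputs the power gain is about 0 points if size is weakly prognostic, 1 to 2 at a log odds ratio of 0.5 per SD, and 2 to 6 at 1.0. The last range needs a strong effect of size, for which the documents offer no evidence.

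The better reason to include size is the two sets defined by sampling success, where balance is not assured. Adjustment would address only the part of that selection that runs through size; it would not restore a randomised comparison.

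**What to change.** Provided lesion size is recorded as a value, name it in SAP I.3 as a prespecified covariate in both the logistic and the ordinal model, alongside age and indication. Enter it as continuous, log-transformed or with a simple spline, and fix the form in advance. State that the adjusted estimate is a conditional odds ratio, and, if precision on an interpretable scale is wanted, report a standardised risk difference with it. Leave the primary chi-squared test as it is.

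The cost is one degree of freedom, or a few with a spline, plus SAP wording that can go into the official plan foreseen in I.6. Prespecification also avoids a decision to add size only after an imbalance has been seen. If only the yes/no eligibility check was recorded, the values would have to be retrieved; if that is not possible, the SAP should say why size is left out.

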#### **I.2.2 Secondary endpoints**

Technical success, pathological classification on which diagnosis was based, and safety (i.e. adverse events) will be compared between the two arms, using the Pearson's chi-squared test. Additionally, the p-value, adjusted by strata, will be calculated. Differences in quality and the presence of tissue cores of both arms will be tested using the non-parametric test for ordinal outcomes. Kappa values will be calculated to determine inter-observer variability among pathologists.

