#### **I.4 Analysis Population**

All analysis will be performed on an intention-to-treat (ITT), modified ITT, and per protocol population. The ITT population are patients that were randomised in the study. The modified ITT population is defined as all patients in whom a puncture resulted in the collection of a diagnostic tissue sample. Patients in which a puncture resulted in tissue collection, independent of the quality of the sample (diagnostic or not) are defined as the per protocol population.

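### The unit of analysis for specimen quality and tissue cores is not stated; if it is the vial, the planned analyses ignore within-patient correlation and understate the needle standard error

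*SAP*

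**What the plan says.** The protocol Summary names, among the secondary endpoints, "specimen specifics, such as; quality, presence of tissue cores, and pathological classification", and, under procedural aspects, "the yield of a single needle pass".

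SAP I.2.2 gives the unadjusted comparison: "Differences in quality and the presence of tissue cores of both arms will be tested using the non-parametric test for ordinal outcomes". SAP I.3 gives the adjusted one: "Ordinal logistic regression will be applied to assess differences of quality and presence of tissue cores between the two methods". The covariates for that model, and for the logistic model of accuracy in the same section, include "number of needle passes, vial number, and the presence of an on-site pathologist".

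On who is randomised, SAP I.4 says: "The ITT population are patients that were randomised in the study". The other two analysis populations are also defined as sets of patients.

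Neither document says whether a record in these analyses is a patient, a pass or a vial. Vial number is not defined. No random effect, GEE, clustered variance or rule for summarising several specimens is mentioned.

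**The concern.** The covariate list uses one term that is clearly a count (the number of passes) and a second, separate term, vial number. The second reads most naturally as an index: first vial, second vial, and so on. An index varies within a patient, which would make the vial the record analysed. Quality and core presence are attributes of a specimen, which fits that reading.

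The needle does not vary within a patient, so its effect is a between-patient contrast. Vials from one patient come from the same lesion with the same needle, so a positive correlation between their scores is plausible. Standard ordinal regression, a standard two-sample ordinal test and standard logistic regression all assume independent records. Applied to vials, they would count each patient several times, and the needle p-values would be too small.

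What is at stake is the credibility of the specimen comparisons, which lie close to the trial's rationale: the protocol contrasts cytological samples from one type of needle with histological samples from the other.

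**Working it through.** **Inputs.** From the documents: patients are randomised (SAP I.4), and the models are ordinary ordinal and logistic regression with vial number as a covariate (SAP I.3). Assumed, because the documents give no value: a two-sided 5% level, m = 2 to 4 vials per patient, and within-patient correlation r = 0.1 to 0.7. The plan has no figure of its own to reproduce.

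**Formulas.** For an exposure that is constant within patient:

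- design effect D = 1 + (m − 1)r
- true standard error ÷ naive standard error = √D
- true type I error of a nominal 5% test = 2 × [1 − Φ(1.96/√D)]

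**One case in full.** With m = 3 and r = 0.5, D = 1 + 2 × 0.5 = 2.0 and √D = 1.414. The naive standard error is too small by 1 − 1/1.414 = 29%. The true error is 2 × [1 − Φ(1.96/1.414)] = 0.166.

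**True type I error over the assumed grid (formula):**

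| m | r = 0.1 | r = 0.3 | r = 0.5 | r = 0.7 |
|---|---|---|---|---|
| 2 | 0.062 | 0.086 | 0.110 | 0.133 |
| 3 | 0.074 | 0.121 | 0.166 | 0.206 |
| 4 | 0.086 | 0.155 | 0.215 | 0.266 |

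The ratio √D runs from 1.05 (m = 2, r = 0.1) to 1.76 (m = 4, r = 0.7). With m = 1 the formula returns exactly 0.05.

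**Check by simulation.** A four-category outcome was generated with no needle effect and a patient random intercept, with the correlation set on the latent logistic scale. Each setting had 3000 runs and used a tie-corrected rank-sum test. With 600 patients and vials treated as independent:

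| m | 0.1 | 0.3 | 0.5 | 0.7 |
|---|---|---|---|---|
| 2 | 0.058 | 0.079 | 0.106 | 0.119 |
| 3 | 0.080 | 0.117 | 0.160 | 0.193 |
| 4 | 0.078 | 0.150 | 0.211 | 0.252 |

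These agree with the formula and are mostly a little lower. With zero correlation, in runs with 200 and with 600 patients, the error stayed between 0.045 and 0.054. With variance clustered on patient it lay between 0.042 and 0.059 in every setting.

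**Does the planned covariate help?** An ordinal logistic model adjusted for vial index (200 patients, m = 3, r = 0.5, 757 fits) rejected in 0.160 of runs, against 0.166 from the formula. Adjusting for the index removes a trend across vials. It does not remove what vials from one patient share.

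**The case against.** The strongest counter-argument is that nothing in the documents says the vial is the record. The logistic model for accuracy uses the same list, "adjusted for; age, indication, number of needle passes, vial number, and the presence of an on-site pathologist". Accuracy is judged against a reference based on resection or on work-up and clinical course, which is a patient-level standard. In that model, vial number could well be the count of vials per patient. The three populations in SAP I.4 are also defined as patients. The single-pass yield endpoint hints at data below patient level, but it is a separate endpoint and I.3 gives no model for it. This argument stands to the extent that the by-vial reading is an inference. It does not settle the matter, because populations defined as patients are compatible with several records for each patient.

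Two further objections are fair. At the low end the inflation is slight: 0.062 by formula and 0.058 by simulation for two vials and a correlation of 0.1. Only a protocol summary and a short statistical section are available, and SAP I.6 says that an official analysis plan will be written before the database closes, so the point may be settled there.

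A reader might also infer that patients with more vials are the difficult cases and would distort the result by their extra weight. The documents link vial count to nothing of the kind. All that follows is that, in a by-vial analysis without clustering, patients with more vials weigh more.

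**Conclusion.** The concern holds conditionally. If records are vials, the ordinary ordinal regression, the ordinal test in I.2.2 and the logistic accuracy model understate the needle standard error. The true error of a nominal 5% test is then about 6% to 27%, for 2 to 4 vials per patient and a correlation of 0.1 to 0.7. Both ranges are assumptions, and the direction requires a positive correlation. If there is one record per patient, the standard errors stand. What is left in that case is that no stated rule turns several vials into one quality score and one core score.

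Two stronger readings should be resisted. One is that the SAP definitely analyses vials as independent; it suggests this but does not state it. The other is that the trial's main result is at risk. The primary chi-squared comparison of accuracy is not shown to be affected; the point is confined to secondary endpoints and the additional multivariate models. Within those limits it is worth correcting, since clustering on patient does no harm if each patient turns out to have one record.

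**What to change.** In SAP I.2.2 and I.3, or in the official plan promised in I.6:

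1. State the unit of analysis for each outcome, and define vial number as either an index within patient or a count per patient.
2. For any analysis with more than one record per patient, including the accuracy model if it is run that way, use GEE with patient as cluster and robust standard errors, or a mixed (ordinal) model with a patient random intercept.
3. Do not run the two-sample ordinal test on vial records.
4. If one value per patient is used, prespecify a summary that does not depend on how many vials were taken, for example the first-pass specimen.

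The best of all specimens does not meet the fourth condition, because it favours the arm with more attempts even when the needles are equivalent. As an illustration, assume a 50% chance of a core in each independent vial. Three vials then give 1 − 0.5³ = 87.5% of patients with any core, and two give 1 − 0.5² = 75%. Correlation between vials narrows this gap but does not close it unless the vials are identical.

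The cost is SAP wording and standard procedures, with no new data. The downside is wider confidence intervals for the needle effect than an analysis treating vials as independent would report.
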